## ABBREVIATIONS AND DEFINITIONS

Abbreviation	Definition
ACR	American College of Radiology
ART	Algebraic Reconstruction Technique
CDE	Common Data Elements
CNT	Carbon nanotube
CT	Computed Tomography
FOB	Forward Operating Base
GPU	Graphics Processing Unit
MRI	Magnetic Resonance Imaging
MTF	Modulation Transfer Function
NPS	Noise Power Spectrum
PACS	Picture Archiving and Communication System
ROC	Receiver Operator Curve
s-HCT	Stationary Head Computed Tomography
TBI	Traumatic Brain Injury
TV-ART	Total Variation minimization method with Algebraic Reconstruction Technique
UQI	Universal Quality Index
XCAT	Extended Cardiac-Torso

## 1.0 BACKGROUND AND RATIONALE

### 1.1 Study Synopsis

This investigation will be a single arm, prospective clinical trial evaluating stationary head CT (s-HCT) as a diagnostic tool in patients with known head trauma. We hypothesize that a stationary head CT (s-HCT) system based on the carbon nanotube linear array x-ray source can provide diagnostic quality head CT images. Patients included in the study will be 50 people who have had either a head trauma or a brain bleed and have undergone a head CT in the past 5 days or who will undergo a CT scan of the head.

### 1.2 Disease Background

The diagnosis of traumatic brain injury (TBI) has become of paramount importance in combat casualty care. In a resource poor environment, the lack of advanced cross-sectional imaging modalities such as computed tomography (CT) limits the ability of forward surgical teams to diagnose life threatening head injuries. As a result, the vast majority of patients with head trauma must be transported to facilities with CT or MRI capabilities to better assess the extent of head trauma. This approach leads to medically unnecessary transport of soldiers and potentially delays in appropriate care. Unfortunately, conventional imaging modalities such as ultrasound and conventional radiographs are essentially useless in diagnosing life-threatening conditions in the brain, including intraparenchymal hemorrhage, subdural or epidural hematomas. To achieve the appropriate level of care, advanced imaging modalities are necessary. Current computed tomography systems, unfortunately, are highly complex instruments requiring the rapid rotation of an x-ray tube and detector system. This approach does not lend itself to use except for in well controlled environments, such as within a hospital.

### 1.3 Investigational Imaging Modality

Recently, we have developed the carbon nanotube (CNT) linear x-ray source array. This x-ray generation approach utilizes field emission which allows two primary advantages: precise x-ray pulse control and close physical placement of multiple x-ray sources. A solid state x-ray source array can provide the necessary x-ray projections to generate CT images without any mechanical motion of components. The goal of this study is to evaluate a solid-state no-rotation x-ray CT system for applications in head trauma imaging in the field.

We have designed a solid-state head CT system to enable head CT scanning at Forward Operating Bases (FOBs) and potentially in patient transport vehicles (ambulance or helicopter). A number of mobile dedicated head CT scanners are commercially available. These devices, for the most part, have been used in intensive care unit or otolaryngology clinical applications. Some have been utilized in ambulance settings, requiring significant maintenance and ambulance modification to provide a stable imaging platform. The slip-ring technology that enables these and other modern CT systems allows the transmission of data and power to the rotating source and detector. The slip-ring interface, however, also

[figure not shown]
requires high precision and regular maintenance to preserve transmission, making them unsuitable for FOBs.

A solid-state system could eliminate the mechanical limitations of placing a scanner at an FOB or within a vehicle, and bring the diagnostic device closer to the patient.

The figures below represent the current prototype of the proposed Head CT system. Three, 45 (forty-five) beam x-ray sources individually are positioned opposite a set of three detectors that are positioned similar to Figure 1(b), with the position of the head represented by the ACR phantom (brown cylinder with small inserts). The x-ray tubes, Model IND1645, are manufactured by NuRay (<http://www.nuraytech.com/en/>) and were custom developed for this purpose.

The detectors that will be used are the Xineos 2301 (Teledyne DALSA) (<https://www.teledynedalsa.com/en/products/imaging/medical-x-ray-detectors/xineos-scanning/>), a 7 x 23 cm detector with high sensitivity in the relevant diagnostic x-ray energies. So, the system will consist of a total of three x-ray sources and nine x-ray detectors. The subjects will be positioned on a medical procedure table that will move the subject through the scanning system at the rate of roughly 1 cm per second, during which the necessary x-ray projections will be acquired. The head will be positioned in a carbon fiber head holder from a clinical CT scanner that is secured to the table.

We are estimating approximately 150 projection angles per slice, with less than a minute per slice reconstruction. Radiation dose will be configured as to not exceed that of a conventional head CT, or 2 mSv. The workflow for the system will be similar to that of a conventional CT, such that the patient is positioned within the head holder on the scanner. Then, once scanning begins, the patient will be automatically advanced into the system across the scan range of the head, during which the necessary x-ray projections will be acquired.

#### 1.4 Rationale

The current Neurosurgery and Severe Head Injury guidelines in the Joint Trauma System (JTS) Clinical Practice Guide (CPG) dictate that all moderate to severe head injuries receive a head CT. However, though neurosurgical support is available at Role 3 facilities, CT scanner capability is only available at Role 4. Thus, there is a significant discrepancy need for improved neuroimaging at Role 3 facilities to prevent unnecessary transport to Role 4 facilities at high, unnecessary cost. Imaging TBI patients earlier could also offer more timely transport to the higher level of care necessary to prevent delay of care which may contribute to the patient condition deterioration.

Per the JTS CPG guidelines, subjects with Glasgow Coma Scores from 9 to 12 are considered a moderate level of injury, with severe injury between 3 and 8. Unfortunately, it is also well known that the GCS does not fully capture the extent of TBI, especially in closed head injury. Recently, studies have also shown that identifying intracranial hemorrhage, is an essential component in providing the appropriate level of care and predicting patient outcomes.

Computed tomography (CT) has become one of the most commonly used imaging modalities. The popularity of CT as a diagnostic imaging tool is understandable – no other modality offers 3-D imaging with the same rapidity and soft tissue discrimination as CT. An estimated 62 million CT scans were performed in 2010 in the US. However, these devices remain complex and difficult to deploy in Forward Operating Bases where they are most needed as a diagnostic tool.

## 2.0 STUDY OBJECTIVES

## **2.1 Primary Objectives**

To estimate sensitivity of stationary head CT for the detection of a hemorrhage using a reader study.

## **2.2 Secondary Objectives**

- To estimate specificity of stationary head CT for the detection of a hemorrhage using a reader study.
- To estimate sensitivity of stationary head CT for the detection of a fracture using a reader study.
- To estimate specificity of stationary head CT for the detection of a fracture using a reader study.
- To evaluate the reader confidence for the stationary head CT in detecting hemorrhage or fracture as compared to a conventional CT.

## **2.3 Outcome Variables**

Sensitivity of stationary head CT for the detection of a hemorrhage using a reader study is defined as the ability of readers (radiologists) to use the stationary head CT to predict hemorrhage using the clinical assessment at 3 months as the gold standard. The interpretation of the clinical data will be made by the study PI ([name]). A neuroradiologist ([name]) may re-interpret images as necessary at the request of the PI.

## **3.0 PATIENT ELIGIBILITY**

### **3.1 Inclusion Criteria**

[figure not shown]
- 3.1.1** 18 years of age or older
- 3.1.2** Medically stable ambulatory patient (outpatient) with head trauma or known intracranial hemorrhage (subdural or intraparenchymal) or skull fractures
- 3.1.3** Patient has undergone conventional head CT imaging at UNC hospitals within the past 5 days or will undergo a CT scan of the head
- 3.1.4** Willing and able to provide written informed consent

### **3.2 Exclusion Criteria**

- 3.2.1** Unable to provide consent
- 3.2.2** Severe claustrophobia

## **4.0 STUDY PLAN**

#### 4.1 STUDY SCHEMA

#### 4.2 Study Procedures

##### 4.2.1 Enrollment/Recruitment

We will recruit 50 medically stable patients who have undergone conventional head CT imaging for imaging within 5 days with the s-HCT system. We will recruit medically stable patients with head trauma or known intracranial hemorrhage (subdural or intraparenchymal) or skull fractures with recent CT imaging. Subjects will be serially recruited with the assistance of the neurosurgery department at our institution. If the attending physician deems a patient stable, a clinical coordinator will obtain informed consent from the subject. If the coordinator has questions about patient competency to provide informed consent, a qualified healthcare provider will make the appropriate determination. In some cases, patients may have recently suffered from a trauma and may be seen for a follow up appointment. In these cases, the s-HCT scan may be obtained prior to the follow up head CT as long as it meets the 5 day window.

Given our high institutional volume of ruptured brain aneurysms and our Level I trauma status, we do not anticipate difficulty with patient volume.

Participants' involvement is limited to one single visit, which will include the s-HCT scan. No follow-up is necessary.

##### 4.2.2 Research Imaging Procedures

Once the study participant has signed the consent forms, either the research coordinator or the radiology technologist will escort them to the study room for the imaging exam.

The participant will not wear any head jewelry during the scan. The participant will have the s-HCT scan performed in a similar manner as the clinical head CT. They will lie on the patient table, and the technologist will position their head in the s-HCT system. Once positioned, the total scan time is a few minutes. The length of time for the positioning and examination may vary, but it is expected that the entire imaging procedure will take about 5-10 minutes, including the positioning time.

##### 4.2.3 Medical Record Abstraction

Data will be collected from participants and their medical records, as applicable. We will follow participants' medical records for 3 months following imaging to

assess for treatment decisions and clinical gold standard as to the presence of a hemorrhage or fracture.

We will document clinical information using the TBI common data elements (CDE) and a local data research electronic data capture system (REDCap). However, as these patients and their imaging data are obtained in a sub-acute setting and from a variety of pathologies, we will not utilize the full TBI CDE data documentation. Specifically, we will utilize the General Core, Demographics, and Injury Presentation. Our clinical scans adhere to the Imaging Diagnostic Imaging Parameters for MRI and Protocols for MRI and CT Guidelines.

#### 4.2.4 Reader Study

All images will be de-identified before inclusion within a reader study. We will perform a reader study with physician readers comparing the acquired imaging s-HCT images and conventional head CT. We hypothesize that the sensitivity of reader's in the interpretation of images from the s-HCT system will be similar to that of the conventional CT imaging. The paired images will be presented to five readers. Readers will be blinded to which imaging modality is being presented. There is, however, readers may be able to distinguish the imaging modality based on the images. Our readers will consist of a trauma surgeon, neurosurgeon or neuro radiologist and non-study radiologists to better reflect the different clinical backgrounds that may be available in a Role 3 environment.

Reconstructed images will be presented in a clinical PACS environment. The readers will be presented images for interpretation in a two-phase study with an interim washout period. First, for each patient, either the s-HCT or conventional head CT images will be presented in random order, and the readers will be asked to identify the presence of hemorrhage (yes/no), the location of the pathology if present and confidence level (0 through 100% in 10% increments). Readers will also be asked to perform interpretations with the appropriate Imaging CT CDE, including the Marshall CT TBI classification code 30, hemorrhage and fracture elements. Four weeks later, the other modality for each patient will be presented in a random order and the same scoring obtained.

The scoring scheme used by readers will include 1) hemorrhage (yes/no) with confidence 0-100% in 10% increments, 2) fracture (yes/no) with confidence 0-100% in 10% increments, 3) streak artifacts (yes/no), and ) other artifacts (yes/no).

### 4.3 Time and Events Table

	Pre-study	Imaging Visit	Conclusion of all data collection
Informed Consent		X	

SOC Imaging	X		
Research Imaging		X	
Medical Record Abstraction/ Questionnaires		X	
Reader Study			X

## 5.0 INVESTIGATIONAL DEVICE

### 5.1 Investigational Device Description

The basic system geometry requirements includes a 25 cm field-of-view and the capability of scanning a 30 cm axial field of view. The approximate power is 1.2 kW. Reconstruction time is estimated to be significantly less than one minute for 40 slices.

The research images will not be interpreted or analyzed for clinical decisions related to the patient. As such, this study will request that the IRB make a determination that this study is no greater than minimal risk. This study meets all the requirements for an NSR determination including:

- The device will not be implanted.
- The device is not intended to support or sustain human life.
- The device is not being used of substantial importance in diagnosing, curing, mitigating, or treating disease.
- The device does not present a potential for serious risk to health, safety, or welfare of a subject.

### 5.2 Expected Risks

Radiation dose will be no more than a conventional head CT (2 mSv), which is considered negligible risk by the Radiation Safety Committee and Institutional Review Board at our institution. All appropriate Institutional Review Board, Electrical and Radiation safety approvals will be obtained prior to the commencement of imaging.

Practically, we anticipate that many of the scans will be obtained in a subacute post-trauma / event time frame, to insure there is no additional risk to the subjects due to subject transport.

Claustrophobia (fear of being enclosed in tight spaces) may occur during the procedure and the noise of the x-ray machine could be uncomfortable. Some people may feel discomfort lying on the CT table or may experience anxiety while the table slides in and out of the CT scanner.

## 6.0 UNANTICIPATED CONCERNS (DEVICES)

## **6.1 Unanticipated Adverse Device Effect (UADE)**

The investigational device exemption (IDE) regulations define an unanticipated adverse device effect (UADE) as “any serious adverse effect on health or safety or any life-threatening problem or death caused by, or associated with, a device, if that effect, problem, or death was not previously identified in nature, severity, or degree of incidence in the investigational plan or application (including a supplementary plan or application), or any other unanticipated serious problem associated with a device that relates to the rights, safety, or welfare of subjects” (21 CFR 812.3(s)).

## **6.2 Unanticipated Problems (UP)**

As defined by UNC’s IRB, unanticipated problems involving risks to study subjects refers to any incident, experience, or outcome that:

- Is unexpected (in terms of nature, severity, or frequency) given (a) the research procedures that are described in the protocol-related documents, such as the IRB-approved research protocol and informed consent document; and (b) the characteristics of the subject population being studied;
- Is related or possibly related to a subject’s participation in the research; and
- Suggests that the research places subjects or others at a greater risk of harm (including physical, psychological, economic, or social harm) related to the research than was previously known or recognized.

## **6.3 Reporting**

### **6.3.1 UADEs**

UADEs must be reported by the clinical investigator to the reviewing IRB, as described below:

For this device study, investigators are required to submit a report of a UADE to the FDA, the manufacturer of the device and the UNC IRB as soon as possible, but in no event later than 10 working days after the investigator first learns of the event (§ 812.150(a)(1)), using the MedWatch Form 3500A. The sponsor-investigator must immediately conduct an evaluation of a UADE and must report the results of the evaluation to FDA, the UNC IRB, and participating investigators within 10 working days after the sponsor-investigator first receives notice of the effect (§§ 812.46(b), 812.150(b)(1)).

For this device study, we will submit a report of a UADE to the manufacturer and the IRB as soon as possible, but no later than 10 working days after the investigators first learn of the event.

### 6.3.2 UP

Any events that meet the criteria for “Unanticipated Problems” as defined by UNC’s IRB must be reported by the Study Coordinator using the IRB’s web-based reporting system.

Any unanticipated problem that occurs during the conduct of this study and that meets **at least** the first two criteria listed in section 6.2 must be reported to the UNC IRB using the IRB’s web-based reporting system.

## 7.0 STATISTICAL CONSIDERATIONS

### 7.1 Study Design

This is a single arm, non-randomized study to calculate sensitivity and specificity for stationary head CT for the detection of a hemorrhage and fracture using a reader study.

### 7.2 Sample Size Rationale

[figure not shown]
For an equivalence test of the difference between conventional HCT and s-HCT, a sample size of 25 subjects achieves at least 80.0% power at a significance level of 0.050 when the lower equivalence difference is -0.237, the upper equivalence difference is 0.237, sensitivity of conventional HCT and s-HCT is assumed to be 90.0%, and the proportion of concordant pairs is assumed to be 0.900.

A table of power calculations for various values of N and various equivalence differences is shown below. For reference, a recent review of the sensitivity of skull radiographs to intracerebral hemorrhage gives a sensitivity range of 3 to 75%.

Power	N	Lower Equivalence	Upper Equivalence	CHCT Sensitivity	s-HCT Sensitivity	Concordance	Alpha
0.99969	25	-0.4	0.4	0.9	0.9	0.9	0.05
1	50	-0.4	0.4	0.9	0.9	0.9	0.05
1	75	-0.4	0.4	0.9	0.9	0.9	0.05
1	100	-0.4	0.4	0.9	0.9	0.9	0.05
0.99906	25	-0.38	0.38	0.9	0.9	0.9	0.05
1	50	-0.38	0.38	0.9	0.9	0.9	0.05
1	75	-0.38	0.38	0.9	0.9	0.9	0.05
1	100	-0.38	0.38	0.9	0.9	0.9	0.05
0.9974	25	-0.36	0.36	0.9	0.9	0.9	0.05
1	50	-0.36	0.36	0.9	0.9	0.9	0.05
1	75	-0.36	0.36	0.9	0.9	0.9	0.05
1	100	-0.36	0.36	0.9	0.9	0.9	0.05
0.99346	25	-0.34	0.34	0.9	0.9	0.9	0.05
1	50	-0.34	0.34	0.9	0.9	0.9	0.05
1	75	-0.34	0.34	0.9	0.9	0.9	0.05

1	100	-0.34	0.34	0.9	0.9	0.9	0.05
0.98497	25	-0.32	0.32	0.9	0.9	0.9	0.05
0.99999	50	-0.32	0.32	0.9	0.9	0.9	0.05
1	75	-0.32	0.32	0.9	0.9	0.9	0.05
1	100	-0.32	0.32	0.9	0.9	0.9	0.05
0.96829	25	-0.3	0.3	0.9	0.9	0.9	0.05
0.99996	50	-0.3	0.3	0.9	0.9	0.9	0.05
1	75	-0.3	0.3	0.9	0.9	0.9	0.05
1	100	-0.3	0.3	0.9	0.9	0.9	0.05
0.93837	25	-0.28	0.28	0.9	0.9	0.9	0.05
0.99979	50	-0.28	0.28	0.9	0.9	0.9	0.05
1	75	-0.28	0.28	0.9	0.9	0.9	0.05
1	100	-0.28	0.28	0.9	0.9	0.9	0.05
0.88916	25	-0.26	0.26	0.9	0.9	0.9	0.05
0.99902	50	-0.26	0.26	0.9	0.9	0.9	0.05
1	75	-0.26	0.26	0.9	0.9	0.9	0.05
1	100	-0.26	0.26	0.9	0.9	0.9	0.05
0.81472	25	-0.24	0.24	0.9	0.9	0.9	0.05
0.99623	50	-0.24	0.24	0.9	0.9	0.9	0.05
0.99996	75	-0.24	0.24	0.9	0.9	0.9	0.05
1	100	-0.24	0.24	0.9	0.9	0.9	0.05
0.71079	25	-0.22	0.22	0.9	0.9	0.9	0.05
0.98761	50	-0.22	0.22	0.9	0.9	0.9	0.05
0.99969	75	-0.22	0.22	0.9	0.9	0.9	0.05
0.99999	100	-0.22	0.22	0.9	0.9	0.9	0.05
0.57643	25	-0.2	0.2	0.9	0.9	0.9	0.05
0.96515	50	-0.2	0.2	0.9	0.9	0.9	0.05
0.99816	75	-0.2	0.2	0.9	0.9	0.9	0.05
0.99993	100	-0.2	0.2	0.9	0.9	0.9	0.05

Here is a plot as a function of N and the equivalence difference.

All power calculations were conducted using PASS 2020 software.

### 7.3 Data Analysis Plans

We will estimate the sensitivity and specificity from the two modalities. To compare the results from the two imaging modalities, we will adopt the mixed effect ANOVA based on the Dorfman-Berbaum-Metz method. To test the main hypothesis, the F-test statistic from the model parameter estimates will be used to compare the mean sensitivity / specificity metrics between the conventional head CT and the simulated solid-state head CT. Possible interactions between the modalities and the readers and the hemorrhage type/locations will also be included and tested for statistical significance. Sensitivity and specificity on the presence of clinically actionable pathology will also be assessed, based on consensus read of the conventional imaging.

For each confidence comparison, the average confidence scores and the corresponding standard deviations will be reported. To test whether the mean

confidence score is larger than zero, a linear mixed effect will be used to analyze data, where the outcome variable is the confidence scores collected in this study and only a grand mean parameter is in the independent list. Additionally, a random intercept is used in the model to account for the correlation among readers when reading the images from the same patient. The Wald's test based on model fit will be used to test whether the grand mean parameter is larger than zero. When the p-value from this test is less than 0.05, it will be concluded that there exists significant evidence that readers have more confidence with the s-HCT modality compared to the other modality. ROC curves will be evaluated.

We will also descriptively compare inter-reader agreement by modality for image quality, confidence in image interpretation, presence and location of hemorrhage, and presence and location of fractures by computing and reporting Fleiss' kappa.

All statistical estimates of population parameters will be tabulated along with corresponding confidence intervals (CIs) and/or standard errors (SEs) to convey levels of precision / imprecision. Hypothesis tests that are deemed to be not statistically significant will be indicated as inconclusive.

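### Section 7.2 sizes the study for a paired equivalence test, but Section 7.3 plans a no-margin F-test for a difference; neither result of that test can support similarity, and the stated 80% power does not belong to it

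*Combined protocol and SAP*

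**What the plan says.** - **Sample size (7.2).** "For an equivalence test of the difference between conventional HCT and s-HCT, a sample size of 25 subjects achieves at least 80.0% power". The limits are ±0.237, the level is 0.050, both sensitivities are taken as 90%, and 0.900 of pairs are taken as concordant. There is no reader term.
- **Analysis (7.3).** The modalities are compared by a mixed-effect ANOVA of the Dorfman-Berbaum-Metz type. "To test the main hypothesis, the F-test statistic from the model parameter estimates will be used to compare the mean sensitivity / specificity metrics" between them. No equivalence limits appear, and the main hypothesis is not defined.
- **Rule for non-significance (7.3).** "Hypothesis tests that are deemed to be not statistically significant will be indicated as inconclusive". Confidence intervals and/or standard errors are promised for all estimates, with no level and no link to ±0.237.
- **Hypotheses.** Section 4.2.4 expects that the sensitivity of readings "from the s-HCT system will be similar to that of the conventional CT imaging". Section 1.1 states a different, non-comparative hypothesis: that the system "can provide diagnostic quality head CT images".
- **Objectives.** The primary objective is estimation: "To estimate sensitivity of stationary head CT for the detection of a hemorrhage using a reader study". The only comparative objective in Section 2.2 concerns confidence: "To evaluate the reader confidence for the stationary head CT in detecting hemorrhage or fracture as compared to a conventional CT".
- **Readers (4.2.4).** "The paired images will be presented to five readers".

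**The concern.** An equivalence test and a test for a difference have opposite null hypotheses. The first rejects when the data exclude a difference as large as the margin; the second rejects when the data exclude zero. Section 7.2 powers the first and Section 7.3 plans the second.

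Two things are at stake. The only justification of the sample size describes a test that is not in the analysis plan. And the similarity hypothesis has no prespecified rule by which it could be met, so a similarity claim drawn afterwards from whichever interval is tabulated would rest on a level and a criterion chosen after the data were seen.

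**Working it through.** **1. Reproduce the stated power.** From 7.2: n = 25, D = 0.237, sensitivities 0.90 and 0.90, concordance 0.90. The two discordant probabilities are therefore 0.05 each and the true difference is 0. Use the paired score test, with the variance estimated under the null, in two one-sided tests at 0.05.

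- The restricted estimate q of the smaller discordant probability solves 2q² + (2D − 0.1)q − 0.05·D(1 − D) = 0, giving q = 0.02167.
- Null SE: s0 = √[(2q + D − D²)/n] = √(0.22416/25) = 0.0947.
- SE under the design assumption: s1 = √(0.10/25) = 0.0632.
- Power = 2Φ[(D − 1.645·s0)/s1] − 1 = 2Φ(1.285) − 1 = **0.801**.

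The same formula returns the table rows 25/0.24 (0.81472), 25/0.20 (0.57643) and 50/0.20 (0.96515). So the arithmetic in 7.2 is right, for two one-sided tests at 0.05, which correspond to a 90% interval. At 0.025 per side (a 95% interval), power at 25 is 2Φ[(0.237 − 1.960 × 0.0947)/0.0632] − 1 = 0.584.

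**2. Set the possible results of the planned test against the similarity hypothesis.**

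| F-test result | What 7.3 lets one say | Supports similarity? |
|---|---|---|
| Significant | The modalities differ | No |
| Not significant | Inconclusive | No |

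**3. How often the two criteria part when the modalities are equal.** Exact multinomial enumeration under the 7.2 assumptions, one read per patient. The documents do not say how many patients will be hemorrhage-positive, so 25 and 50 pairs are assumptions. An uncorrected McNemar test at 0.05 stands in for the F-test; 7.3 states no level for the F-test, so 0.05 is taken from 7.2.

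| | 25 pairs | 50 pairs |
|---|---|---|
| Equivalence criterion met | 88.0% | 99.5% |
| Difference test not significant | 97.8% | 95.3% |
| Equivalence met and difference test not significant | 88.0% | 95.2% |
| Equivalence met and difference test significant | 0.0% | 4.3% |

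The exact figure of 88.0% at 25 pairs exceeds 80.1% because the latter is a normal approximation. With exact McNemar, non-significance rises to 99.9% and 99.1%.

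**4. Does the stand-in matter?** Not for equal modalities, where the rejection rate of any valid test is at most about its level. A simulation of the five-reader Dorfman-Berbaum-Metz F-test (4,000 trials per setting, four assumed correlation structures, 25 or 50 positive cases) rejected in 4.5% to 6.1% of trials. Reading the same model through a 90% interval against ±0.237 declared equivalence in about 99% to 100%.

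**5. Unequal modalities (0.90 v 0.80, 50 positive cases).** The stand-in matters here. Single-read McNemar is significant in 33% to 75% of trials (uncorrected) or 24% to 38% (exact), with detections by s-HCT alone assumed at 0 to 5%. The simulated five-reader F-test is significant in 59% to 84%. In 49% to 82% of all simulated trials it is significant while the 90% interval lies wholly inside ±0.237.

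**6. Two single data sets.**
- 25 pairs, discordant 1 v 1: equivalence p = 0.005 on each side, difference p = 1.0. The 7.2 criterion is met; 7.3 says inconclusive.
- 50 pairs, discordant 6 v 0: larger equivalence p = 0.026, difference p = 0.014. The 7.2 criterion is met; 7.3 says the modalities differ.

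**The case against.** The best defence is that the study is mainly one of estimation. The sensitivity and specificity objectives in 2.1 and 2.2 and the design statement in 7.1 ask only for estimates, and 7.3 never says that its main hypothesis is the one in 4.2.4. This stands as a limit on scope: those estimates are reported whatever the F-test shows, and the label inconclusive attaches to a test, not to the whole trial. It does not remove the mismatch. If the non-comparative hypothesis of 1.1 is meant instead, a between-modality F-test cannot address that either.

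The rule on non-significance is also a safeguard: it prevents absence of a significant difference from being presented as similarity. That is true, and it is exactly why the planned test has no route to the similarity conclusion.

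The margin is already printed in 7.2 and intervals are promised in 7.3, so little would have to be invented later. In part this stands. But the promise is of intervals and/or standard errors, and neither the level nor the decision rule is fixed. The choice between a 90% and a 95% interval moves the 7.2 power from 80.1% to 58.4%.

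Finally, the 95% figure is simply one minus the test level, and a difference that excludes zero can lie inside a margin without logical contradiction. Both points are correct. The figures measure how far the planned test is from the one that was powered; they do not show a defect in the ANOVA model, which is usable.

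**Conclusion.** The concern holds and should be fixed. The 80% power in 7.2 is correctly computed, but for a test that 7.3 does not contain. Under the same assumptions a valid 0.05-level difference test rejects in about 5% of trials or fewer, and a rejection would count against similarity. If the main hypothesis is the one in 4.2.4, no result of the planned test can support it.

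The conclusion about the text needs no numerical assumption. The single-read percentages assume 25 or 50 hemorrhage-positive pairs, the discordance in 7.2 and a 0.05 level for the F-test. The five-reader figures also depend on correlations that the documents do not give; the roughly 5% rejection rate under equality does not depend materially on them. The estimation objectives are not affected.

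**What to change.** Define the main hypothesis in 7.3, then bring 4.2.4, 7.2 and 7.3 into line in one of two ways.

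1. **Keep similarity.** Prespecify that it is met if the confidence interval for the s-HCT minus conventional difference in reader-averaged hemorrhage sensitivity, from the planned multi-reader model, lies wholly within the equivalence limits. Make the F-test supplementary, and say how a difference that is significant but inside the limits will be reported. Fix the interval level in advance (90% matches 7.2). Justify the limits as a meaning of similar: against 90%, ±0.237 admits a true s-HCT sensitivity down to just above 66.3% (0.900 − 0.237 = 0.663). Restate power for this rule with five readers, stated variance components and a range for the number of hemorrhage-positive patients. That number matters: the one-read test in 7.2 has 34% power at 15 pairs, 63% at 20, 80% at 25 and 99.5% at 50 (normal approximation).
2. **Make estimation the whole aim.** Remove the similarity hypothesis and the equivalence power statement, label the F-test exploratory, and justify N by precision. With one read per patient, the exact 95% interval is 78.2% to 96.7% for 45/50 and 68.8% to 97.5% for 22/25.

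The cost is protocol and SAP wording plus a short power or precision calculation, done before the reader data are analysed. No new data are needed. Under the first option the restated power may differ from 80%.
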